There has been some experience with implementing this PMTCT-ART approach, notably in Malawi and Mozambique. In Malawi, recent scale-up of PMTCT-ART was rapid (Figure 1a), with a 12-month postpartum retention of 77%; the majority of those not retained were lost to follow-up (Figure 1b) (1). With increasing momentum to attain 'virtual elimination' of MTCT (e-MTCT) by 2015, more women will be initiated on PMTCT-ART which contributes to decreased infant transmission and sexual transmission (2). Over 1.5 million pregnant women globally were estimated to require PMTCT in 2011(3).

Figure 1a. PMTCT-ART in Malawi(1)

[figure not shown]
[figure not shown]

Figure 1b. Proportion lost to follow-up (Chimbwandira MMWR 2013)(1)

Retention in PMTCT Programs Declines throughout the PMTCT Cascade

In a systematic review of 33 studies from African ART programs in 2007, 2-year retention was estimated to be 61.6% ranging from 24% (worst scenario) to 77% (best scenario). Kenya average 2 year retention in this review was estimated at 66% (4). A review of 18 PMTCT studies noted loss to follow-up rates ranging from 19% to 89.4% whereas Kenyan loss to follow-up rates were ranged from 27% to 80% (5, 6). Initial efforts to enhance PMTCT coverage focused on HIV diagnosis, the first step to enter the PMTCT cascade – which was addressed by rapid, point-of-care, ‘opt-out’ testing (7). The next drop-off in the PMTCT cascade occurs in defining ART eligibility due to lags in obtaining CD4 results; this drop-off will be overcome by PMTCT-ART (8, 9). Post-ART retention is being estimated in programs implementing PMTCT-ART, however long-term data are lacking.

ART Adherence Declines Postpartum and May Compromise PMTCT-ART Effectiveness

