- Phase 2: RCT phase, a triple-arm RCT to evaluate two mHealth interventions designed to enhance long-term ART adherence in PMTCT-ART programs.
- Phase 3: Post-RCT phase, IDIs with RCT participants, clinic health providers, study nurses, and surveys with male partners of RCT participants.

a) STUDY AREA DESCRIPTION:

The proposed study will be conducted at six sites in Kenya: the Ahero sub-District Hospital, Bondo District Hospital, Siaya County Referral Hospital and Rachuonyo sub-County Hospital in Nyanza region and Mathare North City Council Clinic and Riruta Health Centre in Nairobi. These are all high volume government-run public health facilities which serve low- to middle-income rural (Bondo, Ahero, Siaya and Rachuonyo) and peri-urban (Mathare and Riruta) populations. From our previous studies at these sites, HIV seroprevalence among pregnant women is 15% at Mathare and 19% Ahero and Bondo. These four sites provide a wide range of ANC, postnatal care, and HIV services in their catchment areas.

An overview of all study procedures is shown in Figure 3.

Figure 3: Overview of study procedures

PHASE 1: FORMATIVE PHASE

a) STUDY DESIGN

FGDs and IDIs

FGDs are an effective technique to compare experiences and views between participants, and gather the “group effect”, rather than relying on individual data (36). They also provide a breadth and depth of information regarding social norms such as acceptability, which is imperative for successful interventions. IDIs are useful because they provide much more detailed information than what is available through other data collection methods, such as surveys. They may also provide a more relaxed atmosphere in which to collect information and people may feel more comfortable having a conversation (37). IDIs and FGDs will be conducted by a Kenyan team trained in qualitative research methods and will probe for further elaboration on relevant content from the semi-structured FGD guide. Study investigators experienced in qualitative methods, [name] (site-PI) and [name] [name] (co-investigator), have reviewed topic guides for content validity and cultural relevance.

b) STUDY POPULATIONS

The formative phase of the study will include three different populations and study designs: female FGDs, male IDIs, and health care provider IDIs. The study participants will be drawn from peri-urban (Mathare, Nairobi) and rural (Ahero and Bondo, Nyanza) regions of Kenya.

Female FGDs:

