Interactive Bidirectional SMS Messaging: SMS will be delivered once weekly to participants. The diagram (Figure 5) on the left shows a screen shot of Mobile WACh SMS interface with dummy messages and data. Pre-programmed messages will be delivered at times and in languages based on patient preferences. They will include a question soliciting a response from the participant. If no response is received, the participant will receive a “check-in” SMS after failing to respond for 2 weeks. The “check-in SMS” will ask if participant is receiving SMS and if she is well. If no response is received from the participant, no further “check-in SMS” will be sent. However, she will continue to receive standard weekly SMS. Participants in the bidirectional messaging group will also have the capability of texting spontaneously to the system. Interactive SMS communication will be responded to and managed by the study nurse at each site.

We have partnered with a local premium rate service provider (PRSP), Shujaa Solutions, to provide SMS dialogue free of charge to participants.

In this RCT, bidirectional SMS dialogue will be managed by study nurses and standard operating procedures (SOPs) will be developed for standardizing responses to the questions received. Thus, study nurses will follow national guidelines and local practice standards to respond. The process will be adaptive as new scenarios unfold with dialogue –a new question not addressed by the SOPs will be discussed by study team and SOP developed if it is a question likely to be encountered repeatedly. Weekly review of the log of SMS narrative will enable standardization, quality assurance, and understanding women’s use of the system and their level of interaction it. Issues to be examined within the bidirectional intervention arm include ability to standardize messaging, time demands, and time-cost.

Figure 5: Screen-shot of mobile WACh SMS interface with drafted data

Controls: The control arm will receive standard education and counseling provided in ANC.

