Eligibility	
 • HIV-infected women \geq 14 years • Daily access to mobile phone and willing to receive SMS • Literacy not required if women have access to a partner/family member whom she would be comfortable to have read her the messages. • Expected continued residence in study area for the study duration • Willing to provide informed consent • Not enrolled in other studies

e) RANDOMIZATION PROCEDURES

Participants will be randomized to: 1) Simple unidirectional SMS messaging, 2) Interactive bidirectional SMS dialogue, and 3) Control, using 1:1:1 allocation. A computer-generated randomization list will be generated using random block sizes in STATA. The allocation codes will then be put in sequentially numbered sealed envelopes. Participants and study will be un-blinded to randomization arms.

f) DATA COLLECTION PROCEDURES

Women will be followed during pregnancy and for two years postpartum; all clinical care will be managed through the existing MCH and CCC infrastructure. Because the study aims to determine mHealth benefits in a routine clinic setting, specific ANC/PMTCT/HIV services will be delivered by the MOH programs with minimal clinic interactions with study personnel. The study team will abstract data regarding clinic attendance, pill refills, infant health and infant HIV status from the PMTCT program registry, labor and delivery ward, pharmacy and peer counselors registers. Viral load and infant HIV testing results will be abstracted from the national electronic viral load dashboard. We will make check-in calls to all participants regardless of study arm at 1 month and 1 year post-EDD. This will be done to ascertain mother's delivery status, infant status, and that phone number is up to date. Check-in calls will be done by data management teams and will call the participants contacts if they fail to reach study participant.

The study visit schedule will be: enrollment (any time in pregnancy), 6 weeks postpartum, then every 6 months up to 24 months. At each visit a standardized questionnaire will be administered using a tablet-based system (Open Data Kit, ODK) developed by the UW Department of

[figure not shown]

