While retention procedures will be minimized in order to avoid contamination of the intervention on retention outcomes, we will obtain phone numbers of contacts and conduct home visits after enrollment to ascertain locator information. This information will be used at the end of the RCT to conduct home visits to re-establish contact for participants who failed to return for appointments and are lost to follow up in order to ascertain 24-month postpartum outcomes. Participants who are not able to attend the 24-month visit at the clinic will have their 24-month visit procedures conducted at the home visit. Figure 6 illustrates study flow from enrollment to follow up.

In addition to collecting data from study participants during the trial, a facility survey will be conducted with a facility manager at each study site to collect information regarding facility characteristics, Option B+ implementation, human resources, service disruption and service management. The purpose is to identify whether facility-level factors associated with participant clinical outcomes. No human-subject data will be collected.

Figure 6: Consolidated Standards of Reporting Trials-CONSORT diagram of RCT design

We will collect patient information at baseline and follow-up visits using:

- Participant surveys: demographics, clinical and sexual history, family planning, disclosure, medication adherence, experience with SMS and technology, intimate partner violence, and depression
- Medical and pharmacy record extraction forms will be completed by data teams: delivery information, infant immunizations, maternal health, infant health, medication adherence, lab forms, pharmacy data, maternal mortality, and infant mortality.

- Viral load and infant HIV test results will be abstracted from the national electronic VL dashboard.

g) VARIABLES: Outcomes, indicators, and source documents

Table 8: RCT Outcomes

Primary Outcomes	Indicator	Source
Retention	Seen at scheduled visits	PMTCT register for scheduled visits
Drug Adherence	Number/ expected	Self-report, pharmacy 6 wk, 6, 12, 18, 24 mos
Maternal viral suppression	HIV RNA	Maternal blood at 6 wk, 6, 12, 18, 24 mos
Maternal drug resistance	OLA	Resistance assay in mothers with viral failure
Infant HIV	HIV testing: DNA on DBS and antibody	HEI register week 6, infant specimens
Infant HIV-free survival	HIV DNA, antibody and mortality	HEI register week 6, Infant specimens 6, 12, 18, 24 mos; verbal autopsy

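### Six clinics recruit, but neither clinic-stratified randomisation nor a clinic term in the primary models is stated, and adjustment waits for observed imbalance

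*Protocol*

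**What the plan says.** Protocol section 10 a) names six clinics, four rural and two peri-urban: "The proposed study will be conducted at six sites in Kenya". Phase 2 c) sizes the trial at 275 women per arm. Phase 2 b) expects 20 eligible women a month at each of four clinics and 35 at each of two.

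Phase 2 e) gives 1:1:1 allocation and two sentences on method: "A computer-generated randomization list will be generated using random block sizes in STATA" and "The allocation codes will then be put in sequentially numbered sealed envelopes". No stratification factor is named in either document.

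The protocol treats clinic as a possible influence in two places. In the two-way arm, "Interactive SMS communication will be responded to and managed by the study nurse at each site". A facility survey in Phase 2 f) is meant to "identify whether facility-level factors associated with participant clinical outcomes".

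On analysis, SAP section 5.2 tests baseline balance with chi-square tests for categorical variables, and clinic is the first row of SAP Table 5.1, with all six sites. Section 5.3 opens by saying that analyses will be adjusted for imbalances between arms at baseline. It does not say what counts as an imbalance. The primary models that follow (GEE with a log-binomial link, log-binomial regression, Cox regression) list no covariates.

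**The concern.** Clinic may predict retention and viral suppression, and in the two-way arm it is also the unit that delivers the intervention. The usual practice is to stratify allocation by clinic and carry clinic in the model. The plan states neither.

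The adjustment rule in SAP section 5.3 does not fill the gap. If allocation is not stratified and the balance test is run at 5% (an assumption, since the SAP gives no threshold), clinic will be flagged in about 1 trial in 20. If allocation is by clinic, it will almost never be flagged, because the arms are balanced by design. Either way clinic usually stays out of the model, and whether it enters is decided after the data are seen. At stake are some precision in each primary comparison and a primary model that is not settled in advance.

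**Working it through.** **The plan's own figure.** For 75% v 85%, two-sided 5%, 80% power, pooled variance:

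n = [1.96·√(2·0.8·0.2) + 0.8416·√(0.75·0.25 + 0.85·0.15)]² / 0.10² = 250 per arm, as in the sample size tables. Then 250 × 1.1 = 275. The formula uses the full variance p(1−p), so differences between clinics are already inside the stated sample size.

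**Inputs.**
- Clinic shares w, from expected recruitment: 20/150 = 13.3% at four clinics and 35/150 = 23.3% at two, or about 37 and 64 women per arm.
- n = 275 per arm.
- Clinic retention rates p: not in the documents, so assumed. Each scenario spaces six rates evenly over a range, with the two larger clinics at the upper end.
- One binary result per woman. The SAP's GEE and Cox models use more detail, so the results are indicative.

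**Formulas.**
- Between-clinic variance B = Σw(p − p̄)²; total T = p̄(1 − p̄); share R = B/T.
- SE without clinic = √(2T/275); SE with clinic = √(2(T − B)/275).
- SD of the arm difference due to chance clinic mix, if one sequence is shared by all clinics = √(2B/275).

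**Worked case, retention 65–85%.** p̄ = 0.1333 × (0.65 + 0.69 + 0.73 + 0.77) + 0.2333 × (0.81 + 0.85) = 0.766. T = 0.766 × 0.234 = 0.1792; B = 0.0048; R = 2.7%. SE without clinic = √(2 × 0.1792/275) = 3.61 points; with clinic, √(2 × 0.1744/275) = 3.56 points.

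| Assumed spread | R | SE without clinic | SE with clinic | Fall in SE | Clinic-mix SD | Power, 10-point difference |
|---|---|---|---|---|---|---|
| Retention 70–80% | 0.7% | 3.65 | 3.64 | 0.3% | 0.3 | 78.2% → 78.4% |
| Retention 65–85% | 2.7% | 3.61 | 3.56 | 1.4% | 0.6 | 79.1% → 80.2% |
| Retention 60–90% | 6.2% | 3.57 | 3.45 | 3.2% | 0.9 | 80.1% → 82.5% |
| Loss 27–80% (extreme) | 13.9% | 4.21 | 3.91 | 7.2% | 1.6 | 66.1% → 72.5% |

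SEs and SDs are in percentage points. Power is Φ(0.10/SE − 1.96) with the same variance in both arms. It compares the two analyses and does not restate the planned power.

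**Which part of the remedy does the work.** I used 4,000 simulated null trials per cell, with assumed blocks of 3, 6 or 9. The simulation error of a 5% rejection rate is about 0.3 points.

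| Allocation and analysis | 65–85%: SD, rejection rate | Loss 27–80%: SD, rejection rate |
|---|---|---|
| One list, no clinic term | 3.62, 5.1% | 4.28, 5.5% |
| One list, clinic term | 3.55, 4.9% | 3.95, 5.4% |
| Stratified, no clinic term | 3.54, 4.2% | 3.86, 3.4% |
| Stratified, clinic term | 3.57, 5.1% | 3.97, 5.2% |

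Type I error is held on one list with or without the clinic term. With one list, the clinic term recovers nearly all the precision. Stratifying and then ignoring clinic gives a conservative test.

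**The case against.** A reader might infer that all six clinics draw from one unstratified sequence, that their loss rates span 27–80%, and that chance clinic mix therefore moves an arm difference by about ±3 points (1.96 × 1.6) against a planned 10. The documents do not support this.

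- **One shared sequence is not stated.** It rests on a singular noun in Phase 2 e). Separate envelope runs are not excluded, and one numbered series could hardly be opened in order at six clinics recruiting together. The difference matters. With one shared sequence, an arm's count at a 110-woman clinic (825 × 20/150) has SD √(110 × 1/3 × 2/3) = 4.9, so a 95% range of about 27–46. If one list were cut into consecutive runs by clinic, 5,000 simulated trials (same assumed blocks) give 35–38, and a clinic-mix shift of only about ±0.2 points even with 27–80% loss.
- **27–80% is not a spread between these clinics.** The protocol's literature review gives it for published Kenyan PMTCT loss. The trial plans on 75% control retention, that is 25% loss, so on that reading every clinic would lose more women than the planned average.
- **±3 against 10 misleads.** The components add in quadrature: √(3.91² + 1.57²) = 4.21.
- **The facility survey asks whether facility factors matter.** It does not state that they do.

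The SAP also tabulates clinic by arm, tests balance and promises adjustment for imbalance. That provision is real, and the stated power does not fall short for want of stratification. What remains is that the adjustment depends on the data and clinic is not a fixed model term.

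**Conclusion.** The point holds as a modest matter of precision and pre-specification. There is no bias, type I error is not inflated, and the planned 250 (275) per arm is unaffected. With clinic in the model the SE of an arm difference falls by about 0.3% to 3% for assumed retention spreads of 70–80% to 60–90%, and by 7% in the 27–80% extreme, which should carry little weight. Nearly all of the gain comes from the covariate, not from stratified lists. If the lists are in fact by clinic, the present models are slightly conservative (rejection rate 4.2% in the 65–85% case).

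The sizes rest on assumed clinic rates, expected recruitment shares and one binary outcome per woman. The call for a clinic term does not depend on how Phase 2 e) is read: it improves precision under one reading and restores the nominal test level under the other.

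**What to change.** - **SAP section 5.3:** replace adjustment triggered by observed imbalance with clinic (six levels) as a pre-specified covariate in every primary arm comparison, or as a stratum in the Cox model for infant HIV-free survival. Name a fallback for non-convergence, for example a Poisson working model with robust standard errors.
- **Protocol Phase 2 e):** state a separate random-block list and envelope series for each clinic. If allocation was done another way, describe what was done.
- **SAP section 1:** it lists three sites and Table 5.1 lists six. Align them, so that the six levels are unambiguous.

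The cost is nil in patients or visits: six short lists instead of one, and five extra model terms. The one practical risk is that the log-binomial models may fail to converge with the added terms.

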Computer Science and Engineering collaborators. Between study visits, data will be obtained from patient records in order to inform personalized, dynamic messaging. For example, if a participant in one of the intervention arms misses an appointment an appropriate SMS will be sent to address this absence and encourage the participant to reschedule. If a participant in the bidirectional arm does not respond after receiving two weekly messages, she will receive a check-in message asking if she is receiving messages. The study nurse will review clinical records daily to check for missed appointments, deliveries, clinic visits, infant immunizations, or any clinic contact from study participants. Delivery information from women will be obtained at 6 weeks postpartum and data abstracted from records at MCH-linked maternity centers. Follow-up will continue until 24 months postpartum.

In order to ensure completeness of clinic record abstraction for the study period, photographs will be taken at study exit of participants' CCC cards. All identifiable information, including name, date of birth, CCC number, ANC number and address will be covered with paper, and the record will be labeled with the participant's study ID only. Photographs will be transferred to a password-protected computer and secure server within 1 day of the photograph being taken and permanently deleted from the device used to capture the image. At the final study visit, in order to verify the data collected during abstraction, we will measure the height, weight, and mid-upper arm circumference of participants and their infants.

We will collect 14 ml maternal plasma samples for CD4 count, HIV viral load, and suspected drug resistance testing for mothers and 0.5 ml for HIV DNA DBS and HIV antibody testing for infants at all study visits. SOPs will be used to guide venipuncture procedure. The study will obtain viral loads for all participants. However, if the Kenyan MOH incorporates routine HIV viral load testing on a national scale and the testing intervals are similar to those proposed by the study, we will utilize viral load results from the standard of care rather than repeat viral loads.

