## 1. STUDY SUMMARY AND AIMS

### Rationale:

In 2013, WHO recommended that all HIV-infected pregnant women receive lifelong antiretroviral therapy for prevention of mother-to-child transmission (PMTCT-ART). This approach provides treatment and prevention benefits but there are concerns about its risks if maternal retention in care or adherence falters. Mobile health (mHealth) SMS (short message system) messaging is an evidence-based intervention that has been shown to significantly decrease treatment failure in adult ART treatment programs in Africa and may provide an inexpensive, feasible approach to enhance PMTCT-ART outcomes while supplementing rather than adding to provider workload. Our overarching hypothesis is that investment in mHealth for retention and adherence in PMTCT-ART will provide cost-effective benefit in sustaining antiretroviral regimen efficacy and durability.

**Design:** A 3-arm, unblinded, randomized clinical trial (RCT) comparing the effects of unidirectional SMS (ie: “push” messaging to participant) vs. bidirectional SMS dialogue between participant and provider vs. control (no SMS) among HIV-infected Kenyan mothers in PMTCT-ART programs.

**Population:** Pregnant HIV-positive women  $\geq 14$  years old and  $\leq 36$  weeks pregnant.

**Sites:** Ahero Sub-district Hospital (Kisumu, Kenya), Bondo District Hospital (Kisumu, Kenya), Mathare North City Council Clinic (Nairobi, Kenya)

**Sample Size:** 825 women will be randomized (275 per study arm)

**Duration:** Follow-up through 2 years postpartum

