## 2. STUDY ENDPOINTS

Primary study endpoints:

1. **Virologic non-suppression** will be defined for the primary endpoint using plasma viral load cut-off HIV RNA  $\geq 1000$  copies/mL for primary endpoint based on sample detection limits. A secondary cutoff at assay limit of detection (20c/ml for plasma and 839c/ml for DBS) will also be assessed.
2. **Retention in care** will be assessed based on medical record review of clinic attendance for scheduled clinical visits. Retention will be defined per participant as the proportion of scheduled visits to date attended within 2 weeks of their scheduled time and will be evaluated at 12 and 24 months postpartum. Loss to follow-up will be defined as no clinical visits for at least 6 months and will be evaluated at 12 and 24 months postpartum. Initial analyses will examine the 0-365 day interval and the 0-730 day interval.
3. **Infant HIV-free survival** will be assessed using infant HIV test and infant mortality data.

Secondary endpoints:

1. **ART adherence** will be assessed based on pharmacy refill data. For each refill period throughout the study, the proportion of days covered will be based on timing of refill collection. Self-reported adherence will also be assessed at study visits using a standardized questionnaire of the number of pills missed in the last 30 days and calculating percent adherence based on the expected number of doses taken. Self-reported adherence will be compared in secondary analyses.
2. **Drug resistance** will be assessed as detection of drug resistance mutations from plasma of women with HIV RNA  $\geq 1000$  copies/mL using the Oligonucleotide Ligation Assay (OLA).

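### Nobody who ascertains the register-based retention endpoints, or makes the check-in calls on delivery and infant status, is masked to arm, although masking them would cost little

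*Protocol*

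**What the plan says.** **Blinding.** Protocol Phase 2, section e) states: "Participants and study will be un-blinded to randomization arms". Protocol section 10 and SAP section 1 also describe an open trial. Neither document names a masked abstractor, caller, verbal-autopsy reviewer or analyst. Protocol section 15 has analyses run on de-identified data, which hides identity but not arm.

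**Endpoints.** SAP section 2 says that retention in care "will be assessed based on medical record review of clinic attendance for scheduled clinical visits". Loss to follow-up is a gap of six months or more without a clinic visit. SAP Table 2.1 lists both as primary endpoints with record abstraction as the source. Infant HIV-free survival, also primary, draws on record abstraction, infant study visits and verbal autopsy.

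**Who collects the data.** Protocol Phase 2, section f) says: "The study team will abstract data regarding clinic attendance, pill refills, infant health and infant HIV status from the PMTCT program registry". Later in that section: "Medical and pharmacy record extraction forms will be completed by data teams". The list of forms that follows does not name clinic attendance.

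**Calls.** The same section says: "We will make check-in calls to all participants regardless of study arm at 1 month and 1 year post-EDD". It adds: "Check-in calls will be done by data management teams and will call the participants contacts if they fail to reach study participant". The calls establish delivery and infant status and confirm the phone number.

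**The nurse.** Phase 2, section a) gives the two-way dialogue to the study nurse at each site. Section f) adds: "The study nurse will review clinical records daily to check for missed appointments". The same review covers deliveries, visits and other clinic contact.

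**Partial safeguards.** Participants' CCC (Comprehensive Care Clinic) cards are photographed at study exit, labelled by study ID only, to check that abstraction is complete. Viral load and infant test results come from a national dashboard. Home tracing waits until study end in every arm.

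**The concern.** Participants and the SMS nurse cannot be masked, and that is not the criticism. The abstractor, the caller and the verbal-autopsy reviewer can do their work without knowing the arm, and the plan does not ask that they be kept from it.

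Register abstraction is not a laboratory measurement. Attendance is spread over several clinic sources, and a visit that is not found is scored as not attended. Two features make unequal finding plausible without bad faith:

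- The nurse's daily review triggers missed-visit messages in the SMS arms only.
- In the two-way arm, sample messages ask whether the woman is coming and whether she has difficulty attending. Replies can reveal a transfer or attendance elsewhere, and the control arm has no such stream. SAP section 5.5 expects silent transfers, and dialogue could make some of them visible in one arm only.

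If that information reached endpoint scoring, an SMS arm could look better retained with no true effect. SAP section 5 has no analysis that would detect this.

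**Working it through.** **1. The roles side by side.**

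| Role | Needs the arm? | Masked in the documents? | Endpoint touched |
|---|---|---|---|
| Participant | Unavoidable | No | All |
| Study nurse | Yes, runs the two-way dialogue | No | Reads attendance records daily |
| Staff opening envelopes or running the SMS system | Yes | No | None directly |
| Register abstractor | No | Not stated | Retention, loss to follow-up, refills |
| Check-in caller | No | Not stated | Delivery and infant status |
| Verbal-autopsy reviewer | No | Not stated | Infant HIV-free survival |

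The middle column is a judgement drawn from the described tasks, not document text.

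**2. The plan's own sample size.** Inputs from Protocol Phase 2, section c): retention 75% against 85%, two-sided 5%, power 80%, 10% attrition.

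n = [1.96 √(2 × 0.80 × 0.20) + 0.8416 √(0.75 × 0.25 + 0.85 × 0.15)]² / 0.10² = (1.1087 + 0.4724)² / 0.01 = 250 per arm.

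250 × 1.10 = 275, as stated. Masking changes neither figure.

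**3. Illustration of sensitivity.** The documents give no missed-record rates, so the rates here are assumptions. Let true retention R be equal in both arms, and let a share m of truly retained women be scored as lost because their visits were not found. Observed retention is then p = R(1 − m).

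With n = 275 per arm, d = p_i − p_c and p̄ the mean of the two:

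- SE₀ = √(2 p̄ (1 − p̄) / n)
- SE₁ = √([p_c(1 − p_c) + p_i(1 − p_i)] / n)
- P(p < 0.05) = Φ((d − 1.96 SE₀)/SE₁) + Φ((−d − 1.96 SE₀)/SE₁)

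Example: R = 0.85, m = 5% in control and 0% in an SMS arm. Then p_c = 0.8075, p_i = 0.85, d = 0.0425, SE₀ = 0.0321, SE₁ = 0.0321. The first term is Φ(−0.64) = 0.26 and the second is below 0.001, so the false-positive rate is 26.2%.

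| True retention | Missed 2% v 0% | 5% v 2% | 5% v 0% | 10% v 5% | 5% v 5% |
|---|---|---|---|---|---|
| 75% | 6.9% | 9.1% | 16.8% | 15.9% | 5.0% |
| 80% | 7.5% | 10.3% | 20.5% | 18.8% | 5.0% |
| 85% | 8.5% | 12.2% | 26.2% | 22.9% | 5.0% |

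(Control first, SMS arm second.)

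At 5% v 0%, the apparent gain is 3.8 points (0.75 × 0.05) to 4.3 points (0.85 × 0.05), against a planned effect of 10 points. With 248 evaluable per arm (275 × 0.9), the extremes of the table move from 6.9% and 26.2% to 6.7% and 24.1%.

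The z-test stands in for the SAP's log-binomial comparison of the proportions lost. It does not model the GEE analysis of individual visits.

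**The case against.** Openness is a declared design choice, and much of the outcome is a comparison of dates in routine records kept by clinic staff outside the study. To score a retained woman as lost, an abstractor must miss every visit across at least six months, so small lapses rarely suffice. The card photographs are an independent record against which abstraction can be checked. The nurse's review is described as a source for messaging, and the extraction forms belong to data teams.

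Much of this stands, and it limits the point. It makes the larger missed-record rates less likely for loss to follow-up. It does less for the on-time visit proportion, where each unfound visit counts. The photographs need contact at exit, so they are least available for women who are lost. A purpose stated for the nurse's review does not bar its use in scoring.

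A reader might infer four stronger things that the documents do not support:

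- **That call persistence and tracing drive the retention endpoints.** Both endpoints are defined from clinic attendance in records. The calls follow one schedule in all arms and bear on delivery and infant status. End-of-study tracing bears on 24-month data.
- **That data teams abstract attendance knowing the arm.** The key sentence seems to lack a word after *study*. Attendance is assigned to the study team, and the data teams' form list omits it. Both steps are inferences from unrestricted wording.
- **That the inflation is large.** With an assumed SD of 0.20 for each woman's on-time proportion, the SE is 0.20 × √(2/275) = 1.7 points, and a spurious 2 to 3 points would give p < 0.05 in 22% to 42% of null trials. Neither input is in the documents, and the calculation does not apply to loss to follow-up.
- **That everyone else should be masked.** Laboratory masking adds little for viral load or HIV DNA. The 24-month visit may take place at home, and the study questionnaires ask about experience with SMS.

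**Conclusion.** The point holds as an avoidable gap in the plan, not as evidence of bias. No passage masks those who ascertain two primary endpoints that depend on searching records, or those who call about delivery and infant status. No passage separates the arm-aware nurse's daily review, or SMS replies, from scoring.

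The size is illustrative: roughly 7% to 26% false positives in place of 5%, if 2% to 5% of truly retained control women's records were missed and none in an SMS arm, with true retention of 75% to 85% and 275 per arm. Equal missed rates give 5.0%, however high they are. A difference in the other direction would hide a benefit. Viral load is little affected.

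**What to change.** Replace the blinding sentence in Protocol Phase 2, section e) with a statement by role, and repeat it in the SAP:

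- Participants, study nurses, and staff who open envelopes or run the SMS system know the arm.
- Register abstractors, check-in callers and verbal-autopsy reviewers work from study-ID lists that do not show the arm.
- Retention, loss to follow-up and refills are scored only from the abstraction forms, checked against the CCC-card photographs where these exist. The nurse's daily review and SMS replies are not used.

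The documents should also say who on the study team abstracts attendance.

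The cost is wording and removal of the arm field from worklists and tools. If study nurses abstract attendance at any site, that task must move to the existing data team. Some women will reveal their arm on a call, so masking of callers will be incomplete.
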